### **13.2 Analysis of Endpoints**

All data will be tested for normality. Normally distributed data will be presented as means  $\pm$  SD. Statistical analyses will be performed on SPSS software version 24.0 (Chicago, IL). For normally distributed data a one-way analysis of variance (ANOVA) will be used to identify differences between conditions for plasma [glucose] (AUC and peak), plasma [insulin], insulin sensitivity, [eHSP70], [IL-6], [IL-10], HRV, NIRS and RMR. Where significance differences are observed, post hoc test will then be performed. Where data is not normally distributed, appropriate non parametric tests will be utilised.

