### **6.2 Secondary Objectives**

*To determine:*

1. whether plasma [glucose] reduces more if the passive, warm water therapy is conducted before or after the OGTT?
2. whether plasma [insulin] reduces more if the passive, warm water therapy is conducted before or after the OGTT?
3. whether insulin sensitivity increases following an acute bout of warm water therapy?
4. whether fuel utilisation alters during and following an acute bout of warm water therapy?
5. whether cardiovascular status is altered during or after an acute bout of warm water therapy?

6. whether eHSP increases during an acute bout of warm water therapy?
7. whether inflammatory status reduces during or after an acute bout of warm water therapy?

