### 6.3 Summary of Study Design

#### Recruitment

Participants will be recruited from adult diabetes outpatient clinics at the Queen Alexandra Hospital (Portsmouth), via a database of known individuals with T2DM from the Wessex, Diabetes, National Institute for Health Research (NIHR) Clinical Research Network and via posters and word of mouth at the University of Portsmouth. Only males and post-menopausal women will qualify for the study. Finally, the local Desmond diabetes awareness group meetings will be used to identify potential volunteers. Potential participants will either be approached by their T2DM consultant, the principal investigator, member of the research team or a research nurse. Following the participants declaration of interest, via telephone, mail, email or in clinic, they will be given a participant information sheet. A member of the research team will subsequently approach the participant  $\geq 48$  h later, to answer any questions and organise consent, screening and familiarisation (visit 1).

The design will be a balanced, randomised, within-subject comparison of three conditions (condition 1: OGTT in 23 °C air, condition 2: OGTT 30 min before 60 min in  $\sim 39^{\circ}\text{C}$  water ( $\sim 90\%$  RH), condition 3: OGTT 30 min after 60 min in  $\sim 39^{\circ}\text{C}$  water ( $\sim 90\%$  RH)). There will be 4 visits in total, visit 1 is for consent, screening and familiarisation and visits 2, 3 and 4 are experimental conditions.

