## 8. SAMPLING

Plasma glucose AUC is our primary outcome. No study to date has assessed the effect of hot water immersion on glucose tolerance in individuals with T2DM. Therefore, no data were available to power our primary outcome. For 90% power with an  $\alpha$ -level set at  $P < 0.05$  (two tailed), to detect a 1 SD difference, 13 volunteers are required to compare within group for placebo and active conditions. In order to counterbalance our design, 18 participants will be required to complete the testing. Therefore, we aimed to recruit 20 individuals with T2DM to account for a 10% drop-out rate typically seen in our clinical trials. Resultant effect sizes will be used to power future trials.

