## **13. DATA ANALYSIS**

### **13.1 Description of Analysis Populations**

Participants who completed all 4 visits will be entered into the analysis.

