### **13.4 Procedures for Reporting any Deviation(s) from the Original Statistical Analysis Plan**

For this study a statistical analysis plan is not required (excluding the above).

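### Section 13.2 names a one-way ANOVA without a participant or repeated-measures term for a within-subject crossover sized as a paired comparison; read literally the test is conservative, and the wording should be completed

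*Combined protocol and SAP*

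**What the plan says.** Section 6.3 (Summary of Study Design) states: "The design will be a balanced, randomised, within-subject comparison of three conditions". Section 8 sizes the trial for glucose AUC at 90% power, two-sided 0.05 and a 1 SD difference, and concludes that "13 volunteers are required to compare within group for placebo and active conditions". This is raised to 18 completers for counterbalancing and to 20 recruits for dropout.

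Section 13.1 restricts the analysis: "Participants who completed all 4 visits will be entered into the analysis". Section 13.2 then names the only test: "a one-way analysis of variance (ANOVA) will be used to identify differences between conditions for plasma [glucose] (AUC and peak"), and applies it to insulin, insulin sensitivity, eHSP70, IL-6, IL-10, HRV, NIRS and RMR as well. The follow-up is "Where significance differences are observed, post hoc test will then be performed", and the fallback is "Where data is not normally distributed, appropriate non parametric tests will be utilised". Section 13.4 adds: "For this study a statistical analysis plan is not required (excluding the above"). No section names a repeated-measures ANOVA, a participant effect, or a period or sequence term.

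**The concern.** Each analysed person contributes one value per condition, so the three sets of values are correlated. A one-way ANOVA run on condition alone treats them as three separate groups and leaves the stable differences between people in the error term. The sample size relies on removing those differences by pairing.

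The p-value for the primary outcome is at stake, as is the width of any interval that uses the ANOVA error. The post hoc comparisons are also affected, because they run only after a significant ANOVA. They include the contrast that secondary objective 1 asks for, "whether plasma [glucose] reduces more if the passive, warm water therapy is conducted before or after the OGTT". Two analysts following section 13.2 could reach different p-values from the same data, and no other text settles which is right.

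**Working it through.** **1. The plan's own figure.** The inputs are from section 8: power 90%, two-sided alpha 0.05, difference 1 SD.

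- Paired t-test, df = n-1, noncentrality d*sqrt(n), d = 1: power is 0.883 at n = 12 and 0.911 at n = 13. The stated 13 is reproduced. At 18 completers power is 0.979.
- Independent groups, df = 2n-2, noncentrality d*sqrt(n/2): power is 0.687 at 13 per group, 0.8997 at 22 and 0.912 at 23. This does not give 13.
- If 1 SD means the SD of the outcome, the paired effect is d = 1/sqrt(2(1-rho)). The required n is 17, 13, 9 and 7 at rho 0.3, 0.5, 0.7 and 0.8. So 13 fits that reading only near rho 0.5, and the calculation is still paired.
- Dropout: 18/0.9 = 20, as stated.

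**2. Error terms.** Assumptions not in the documents: equal outcome variance (sigma squared) in each condition, a common within-person correlation rho, 18 completers with full data.

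- The variance of a difference between two condition means is 2*sigma^2*(1-rho)/18.
- The literal ANOVA estimates it as 2*sigma^2/18, on 3*18-3 = 51 df.
- A repeated-measures ANOVA estimates 2*sigma^2*(1-rho)/18, on 2*17 = 34 df.
- The literal standard error is therefore too large by 1/sqrt(1-rho).
- The unadjusted 95% half-width, in outcome SDs, is 2.008*sqrt(2/18) = 0.67 (literal) against 2.032*sqrt(2(1-rho)/18) (repeated measures).

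**3. Size and power of the overall F test.** Simulated with 100,000 trials per cell, n = 18. Power is for a 1 SD shift in one heated condition; shifting both gives the same to within 0.3 points. RM = repeated measures.

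| rho | SE ratio | Half-width, literal / RM | Type I, literal | Power if 1 SD is SD of paired difference, literal / RM | Power if 1 SD is outcome SD, literal / RM |
|---|---|---|---|---|---|
| 0.3 | 1.20 | 0.67 / 0.57 | 1.6% | 97% / 99% | 89% / 95% |
| 0.5 | 1.41 | 0.67 / 0.48 | 0.4% | 91% / 99% | 91% / 99% |
| 0.7 | 1.83 | 0.67 / 0.37 | 0.04% | 65% / 99% | 94% / >99% |
| 0.8 | 2.24 | 0.67 / 0.30 | below 0.1% | 33% / 99% | 96% / >99% |

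At rho = 0 the literal test has its nominal size (about 5.0%). The RM test stays at about 5% throughout.

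The effect pattern matters. With condition means at 0, -0.5 and -1 SD of the paired difference, literal power is 91%, 77%, 43% and 17% at the four values of rho, against 96% for RM.

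**4. Does pairing the post hoc tests rescue it?** I counted a paired t-test of condition 3 against 1 only when the overall test was significant, with both heated conditions shifted by 1 SD of the paired difference. Power behind the literal ANOVA is 96%, 91%, 65% and 33%; behind the RM ANOVA it is 98%. Paired tests give correct contrast intervals, but the literal overall test still blocks them.

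**5. Is plain repeated-measures ANOVA enough?** The two heated conditions may correlate more with each other than with control. With assumed heated-heated correlation of 0.8 or 0.9 and control-heated correlation of 0.4 or 0.5, uncorrected RM type I error at n = 18 is roughly 6% to 7%. With Greenhouse-Geisser it is about 5%. Where correlations are equal, the correction costs well under 2 points of power (for example 99.1% to 99.0% in the SD-of-difference column).

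**The case against.** The strongest reply is that one-way counts factors and does not mean independent groups: a one-factor repeated-measures ANOVA is also one-way. The crossover design, the within-group sizing and the completers-only population all point to that reading. This stands. The documents do not show that an independent-groups test is intended, and a reader who concludes that the sponsor chose the wrong test goes further than the text allows. What remains is that the structure is not stated and no further plan will state it.

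The second reply is that the harm is limited. This also stands in large part. The literal test does not inflate false positives, it leaves mean differences unchanged with complete data, and the margin from 13 to 18 participants absorbs much of the loss. In six of the eight literal power cells above, power is 89% or more.

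Third, section 19 says that effect sizes and confidence intervals will power a larger study, and one might infer that the later trial will be mis-sized. No section says those estimates will come from the pooled ANOVA error, so I give this no weight.

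Fourth, the promise of appropriate non-parametric tests can fairly be taken to mean related-samples tests. Naming one is clarification only.

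**Conclusion.** The point holds as an incomplete specification of the primary analysis, at should-fix level. The named test lacks the participant term that the design and sample size presuppose. If it is run as written, the primary p-value is wrong in the conservative direction for any positive rho, and contrasts that use the ANOVA error have standard errors too large by a factor of 1.20 to 2.24 over rho 0.3 to 0.8.

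A reader might infer that the trial is underpowered. The documents do not support that as a general statement. For a 1 SD shift in one or both heated conditions, literal power stays near or above 90% unless rho is clearly above 0.5 and 1 SD means the SD of the paired difference. The plan gives neither rho nor the meaning of the SD. A graded effect would lose more. All these figures assume equal variances, a common correlation and 18 complete participants. The finding on the wording and the reproduction of 13 need none of these assumptions.

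**What to change.** In section 13.2:

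- Replace the named test with a one-way repeated-measures ANOVA with Greenhouse-Geisser correction. A mixed model with a participant effect and unstructured covariance across conditions is an alternative. It also keeps a participant who attended every visit but lacks one condition's value, a case that section 13.3 leaves open.
- State that post hoc contrasts are paired. Report paired mean differences with 95% CIs for conditions 2 vs 1, 3 vs 1 and 3 vs 2; the last answers secondary objective 1.
- Name a related-samples (Friedman-type) test as the non-parametric fallback.
- A period term is optional. It takes the error df from 34 to 32 at 18 completers, which widens intervals by about 0.2% if there is no period effect.

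The cost is a few words, with the same software and no new data or participants. If repeated measures was always intended, the edit changes nothing in the analysis except the explicit correction.

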For all visits (see figure 2), participants will lie in a semi recumbent position in minimal clothing (bathing shorts and a t-shirt) for the entirety of the visit. Initially, participants will be cannulated (Versatus winged and ported IV cannula, Terumo, Japan) and blood samples drawn for analysis of osmolality (Lithium Heparin (LH) tubes BD, USA) plasma [glucose] (Fluoride/Oxalate tubes, BD, USA), [insulin] (Ethylenediaminetetraacetic acid (EDTA) K2, BD, USA), and [eHSP70] (EDTA K2, BD, USA) at baseline and every 30 min of each experimental visit. Following cannulation an 180 min OGTT (75g) (RapiLOSE OGTT solution, Penlan healthcare, Japan) will commence in a thermoneutral room (~ 23°C). A maximum of 18 mL of blood being drawn at each time point (max 126 mL per visit). To maintain the patency of the cannula and to reduce the risk of infection, after every sample is taken, 5 mL of saline will be flushed through the cannula. Then before every sample is taken, 2.5 mL of blood will be drawn out of the cannula to ensure any remaining saline will not interfere with the samples and data interpretation (additional 17.5mL per visit). During the OGTT, HR (via electrocardiogram) will be measured continuously, whilst blood pressure (M5-1, Omron, Japan), deep body temperature (rectal probe) and resting metabolic rate (indirect calorimetry) (Quark CPET, Cosmed, Italy) will be assessed every 30 min.

Condition 2 will employ identical procedures to condition 1, except thirty minutes into the OGTT, the participant will be immersed into an immersion tank (~39°C) for 60 min. Water temperature will be manipulated as required to achieve and maintain a target  $T_{rec}$  at 38.5°C using water between 37.5 and 39°C, and then participants will be removed horizontally back into the thermoneutral room for the remainder of the OGTT. Participants will be towel dried and given a towelled robe to wear. Condition 3 will employ identical procedures to condition 2, with the exception that the heating via immersion will start as soon as the participant is instrumented (and following a 15 min rest period) and the OGTT will commence 30 min after the 60 min immersion time for a further 180 min (see figure 2 for a schematic). Finally, if willing participants will be asked to take part in a brief exit interview about their experience.

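### Section 13.2 names a one-way ANOVA with no participant term for a within-subject crossover and does not say whether the primary glucose AUC is total or incremental; separately, the stated blood volume does not fit condition 3

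*Combined protocol and SAP*

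**What the plan says.** **Outcome and test.** Section 8 states: "Plasma glucose AUC is our primary outcome". Section 13.2 says a "one-way analysis of variance (ANOVA) will be used to identify differences between conditions for plasma [glucose] (AUC and peak" and the other listed measures. Post hoc tests follow only where that test shows differences. No participant term is named. No AUC formula, AUC type or baseline sample appears in 13.2, the synopsis or section 8. Section 13.4 says that no statistical analysis plan is needed beyond this text.

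**Design and sample size.** Section 6.3 says: "The design will be a balanced, randomised, within-subject comparison of three conditions". Section 8 says that for 90% power, two-sided 5%, and a 1 SD difference, "13 volunteers are required to compare within group for placebo and active conditions". It then moves to 18 completers for counterbalancing and 20 recruited.

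**Timing.** In condition 2 (section 6.3, visits 2, 3 and 4), "thirty minutes into the OGTT, the participant will be immersed". In condition 3, "the OGTT will commence 30 min after the 60 min immersion time". The Figure 2 caption puts the condition 3 OGTT samples at 1000 to 1300, with an extra sample at 0830. The caption writes visit where it means condition: section 6.3 says "visit 1 is for consent, screening and familiarisation and visits 2, 3 and 4 are experimental conditions". That slip is clerical.

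**Blood volume.** Section 6.3 allows at most 18 mL per time point and 126 mL per visit, plus 2.5 mL discarded before each sample, given as 17.5 mL per visit. Section 9.4 lists seven OGTT samples, at 0 to 180 min.

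**The concern.** Section 13.2 is the only analysis text, so whoever runs the analysis works from it. In statistical software a one-way ANOVA and a one-way repeated-measures ANOVA are different procedures. The first, run on three columns of AUCs from the same people, treats them as three unrelated groups. It discards the pairing on which the sample size rests. Because post hoc tests depend on the omnibus result, a missed omnibus test also closes off the comparisons between conditions. Section 19 says that the effect sizes and confidence intervals will power a larger study, and intervals from the wrong error term would be carried forward.

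The AUC gap matters more here than in most OGTT studies. In conditions 1 and 2, time 0 precedes any heating. In condition 3 it follows heating. An incremental AUC from time 0 would subtract any heat effect already present, in condition 3 only. That touches the comparison of heating with control and the first secondary objective, "whether plasma [glucose] reduces more if the passive, warm water therapy is conducted before or after the OGTT". If the definition stays open, it can be chosen after the data are seen.

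**Working it through.** **1. The plan's sample size.** Inputs from section 8: power 90%, two-sided 5%, difference 1 SD. For a paired t-test with 1 SD of the paired difference, the noncentrality is √n. Exact power is 88.3% at n = 12 and 91.1% at n = 13, so 13 reproduces. Other readings do not give 13:
- normal approximation: (1.960 + 1.282)² = 10.5, so 11
- one-sided t-test: 11
- two independent groups (normal approximation): 2 × 10.5 = 21.0 before rounding up, so 22 per group.

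The first multiple of 6 (the number of orders of three conditions) at or above 13 is 18, and 18/0.9 = 20. The plan's figures hold together, and they presuppose a within-person test.

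**2. Omnibus test with and without a participant term.** Set-up: 18 people, three conditions, total variance 1, within-person correlation ρ (assumed; the documents give none), and one condition differing by 1 SD of the paired difference, δ = √(2(1−ρ)).
- With a participant term, the error variance is 1−ρ on 34 df. Noncentrality = 18 × (2/3)δ²/(1−ρ) = 18 × 4/3 = 24 at every ρ, and power is 99.1%.
- Without it, the error variance includes the between-person part and is about 1, on 51 df: larger by a factor of 1/(1−ρ).

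Simulation, 40,000 trials per row:

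| ρ (assumed) | Error variance ratio 1/(1−ρ) | Power with term | Power without | Type I error without |
|---|---|---|---|---|
| 0.5 | 2.0 | 99% | 91% | 0.4% |
| 0.7 | 3.3 | 99% | 64% | <0.1% |
| 0.8 | 5.0 | 99% | 33% | <0.1% |
| 0.9 | 10.0 | 99% | 3% | <0.1% |

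Type I error with the participant term is about 5% in every row.

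**3. Total against incremental AUC.** Seven samples 30 min apart have trapezoid weights 15, 30, 30, 30, 30, 30, 15, which sum to 180. Hence net incremental AUC = total AUC − 180 × G0, where G0 is the time-0 glucose. This is exact; a version that counts only area above baseline differs if the curve falls below G0. For any contrast between conditions the two definitions differ by 180 × the difference in G0:
- 0.1 mmol/L gives 18 mmol/L x min
- 0.25 gives 45
- 0.5 gives 90
- 1.0 gives 180.

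These shifts are assumptions. If the whole condition 3 curve fell by 0.5 mmol/L, total AUC would fall by 90 and incremental AUC by 0. The signs can also oppose. If time 0 rose by 1.0 and all later values by 0.5, total AUC would change by 15 × 1.0 + 165 × 0.5 = +97.5, and incremental AUC by 97.5 − 180 = −82.5.

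**4. Blood volume in condition 3.** Stated: 126/18 = 7 draws and 17.5/2.5 = 7 discards, in all 126 + 17.5 = 143.5 mL. Scheduled by Figure 2 with section 9.4: 0830 plus seven OGTT samples = 8 draws. 8 × 18 = 144 mL, and 8 × 2.5 = 20 mL, in all 164 mL. The excess is 18 mL on the stated maximum and 20.5 mL with discards.

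**The case against.** **The ANOVA.** One-way counts factors, and condition is the only factor, so a one-way repeated-measures ANOVA is compatible with the text. Sections 6.3 and 8 describe a within-subject comparison, and section 13.1 keeps only people who completed all four visits, which is what a repeated-measures ANOVA needs. A reader might infer that the trial plans an independent-groups test; the documents do not support that. Nor would the literal test produce false positives: it is conservative. All of this stands. What remains is that the only analysis text names a procedure that, run as written, does not match the design.

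**The AUC.** The synopsis speaks of AUC during an OGTT and mentions no baseline subtraction, so total AUC is the plain reading. The plan states no wrong rule. A reader might infer that the plan would subtract away the heat effect in condition 3; nothing says so. A reader might also borrow the fall in fasting glucose that section 4 cites from a hot-tub study to size the shift. That came after three weeks of daily bathing and says nothing about one hour. Alone, this part is mostly missing detail.

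**Blood draws.** The general rule of sampling at baseline and every 30 min of each visit could be read as giving more than eight draws in condition 3. The explicit schedule in Figure 2 answers that reading. The eight-draw mismatch does not depend on it.

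**Conclusion.** The point holds in three parts of unequal weight.

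- **Test.** Section 13.2 is wrong as written for this design, though repeated measures is probably intended. If it were followed literally, omnibus power at n = 18 would fall from about 99% to about 91%, 64%, 33% or 3% at correlations of 0.5 to 0.9. The loss rests on those assumed correlations, on an effect of 1 SD of the paired difference in one condition, and on equal correlation between conditions. The direction does not depend on the exact value: any positive correlation makes the error term too large.
- **AUC.** The definition is open, and condition 3 makes the choice matter. The gap of 18 mmol/L x min per 0.1 mmol/L is exact for net incremental AUC. Whether heating shifts time-0 glucose at all is unknown from the documents, so no bias is shown, only an unfixed choice.
- **Blood volume.** The stated maximum contradicts the plan's own sampling schedule for condition 3. This is separate from the analysis and needs no assumption beyond the per-draw amounts given.

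**What to change.** In section 13.2 write: *The primary outcome is total plasma glucose AUC over 0–180 min of the OGTT (trapezoid rule, seven samples, no baseline subtracted). Conditions are compared by a one-way repeated-measures ANOVA with participant and condition. Incremental AUC is a sensitivity analysis only, with its baseline sample stated.* For condition 3 that statement must choose between the 0830 sample, before heating, and the 1000 sample, after it.

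Reconcile the per-visit volume in section 6.3 with Figure 2 and section 9.4, and restate it for condition 3. Correct the visit labels in the Figure 2 caption at the same time.

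The analysis change costs three sentences, with no extra participants, samples or visits. It should be made before any outcome data are examined.

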**Figure 2.** Schematic of the 3 experimental conditions. BP, thermal sensation, HRV, osmolality, insulin sensitivity, RMR, eHSP70, IL-6, IL-10, plasma glucose and insulin measured at 30 min intervals from 0930-1230 for visit 1 and 2, and from 1000-1300 for condition 3 (with the addition of a baseline measure at 0830 for visit 3). Muscle oxygenation at 0930, 1000, 1130, 1200 and 1230 for condition 1 and 2. Muscle oxygenation at 0830 and from 1000-1300 at 30 min intervals for condition 3. HR continuous for entirety of visit. Solid line indicates immersion period and dashed line indicates OGTT period.

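### The glucose AUC comparison leaves out the pre-heating fasting glucose scheduled at every experimental visit. This loses precision but does not bias the result, and the adjustment needs a safeguard in condition 3.

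*Combined protocol and SAP*

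**What the plan says.** Section 8 names the outcome: "Plasma glucose AUC is our primary outcome". It does not say whether total or incremental area is meant. Section 6.3 describes the design: "The design will be a balanced, randomised, within-subject comparison of three conditions". Section 13.2 then gives a one-way ANOVA that "will be used to identify differences between conditions for plasma [glucose] (AUC and peak") and for the other outcomes, followed by post hoc tests. No covariate, change score or period term is named. Section 13.4 says that nothing beyond this is needed as a statistical analysis plan.

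On sampling, Section 6.3 (Visit 2, 3 and 4) has glucose drawn "at baseline and every 30 min of each experimental visit". The Figure 2 caption lists samples from 0930 to 1230 for the first two conditions and from 1000 to 1300 for condition 3, "with the addition of a baseline measure at 0830 for visit 3". Condition order is randomised, so that last label makes sense only as condition 3. The one stated use of fasting glucose is the QUICKI index in Section 9.4.

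**The concern.** A crossover removes stable differences between people. It does not remove differences between one person's three mornings. The experimental visits are spread over about three weeks (Section 10.4) and diet is replicated by the participants themselves, so some visit-to-visit variation in fasting glucose is plausible. Fasting glucose is also the level from which the 0 to 180 min curve starts. Whatever part of AUC it predicts within a person stays in the error term under Section 13.2, although the value is scheduled at every visit.

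What is at stake is the width of the confidence interval. Sections 8 and 19 say that the effect sizes and intervals will be used to power a larger trial, so precision is itself one of this study's products.

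**Working it through.** **1. The plan's own figure.** Inputs from Section 8: "For 90% power with an" alpha of 0.05, "two tailed), to detect a 1 SD difference, 13 volunteers are required"; then "In order to counterbalance our design, 18 participants will be required to complete the testing", with 20 recruited for 10% dropout. I read 1 SD as the SD of the paired difference and use a two-sided paired t-test with noncentrality d√n on n − 1 df.

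- n = 13, d = 1: power 0.911. n = 12: power 0.883. The stated 13 reproduces.
- 18 = 3 × 6 treatment sequences, and 18/0.9 = 20. Both reproduce.
- n = 18, d = 1: power 0.979.

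**2. Is there a pre-heating value at every visit?**

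| Condition | Heating | OGTT start | Last fasting sample before heating |
|---|---|---|---|
| 1 | none | 0930 | 0930 (0 min) |
| 2 | from 30 min into the OGTT | 0930 | 0930 (0 min) |
| 3 | 60 min, ending 30 min before the OGTT | 1000 | 0830 |

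In condition 3 immersion starts at 1000 minus 90 min = 0830, so its OGTT time-0 sample is taken after heating and is not a baseline.

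**3. Gain from adjustment.** The documents give no r, so 0.3 to 0.7 is an assumed range. Take 18 people × 3 visits = 54 values, with 18 participant, 2 period and 2 condition parameters. Residual df = 54 − 22 = 32, or 31 with the covariate. The contrast variance is multiplied by V = (1 − r²)(1 + 1/30), where the second factor is the price of estimating the slope. Power uses noncentrality 0.6 × √(18/V). The 0.6 SD is also an assumption, on the paired-difference scale.

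| r | V | Equivalent completers, 18/V | Noncentrality at 0.6 SD | Power at 0.6 SD |
|---|---|---|---|---|
| no covariate | 1 | 18 | 2.55 | 0.69 |
| 0 | 1.03 | 17.4 | 2.50 | 0.68 |
| 0.3 | 0.94 | 19 | 2.63 | 0.72 |
| 0.5 | 0.775 | 23 | 2.89 | 0.80 |
| 0.7 | 0.53 | 34 | 3.51 | 0.92 |

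Simulations of the 18-person crossover agree. Variance ratios were 0.94 to 0.95, 0.77 to 0.81 and 0.51 to 0.53, and power was 0.71 to 0.72, 0.80 to 0.81 and 0.92 to 0.93. Type I error was 4.4% to 6.0% when the baselines were exchangeable across conditions. At the planned 1 SD, simulated power goes from about 98.5% to 98.7%, 99.6% and 99.98%.

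**4. Using the wrong sample in condition 3.** Suppose r = 0.6 and heating lowers the OGTT time-0 value by 0.5 paired-difference SD (both assumed). Adjusting for that value turns a true 0.70 SD effect into 0.70 − 0.6 × 0.5 = 0.40 SD. Simulated power falls from 82% to 48%.

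**5. The one-hour difference in clock time.** Suppose fasting glucose at 0830 differs systematically from 0930 by 0.5 within-person SD (assumed), and that this has no bearing on AUC. In paired-difference units the shift is 0.5/√2 = 0.354, and the adjusted condition 3 contrast is biased by r × 0.354.

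- r = 0.5: bias 0.177, standard error √(0.775/18) = 0.21, ratio 0.85. Simulated type I error is about 14%.
- r = 0.7: bias 0.248, standard error √(0.527/18) = 0.17, ratio 1.45. Simulated type I error is about 27%.
- With a 0.25 SD shift the figures are about 7% and 10%.

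The condition 2 versus control contrast uses 0930 samples on both sides and stays near 5%.

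**6. Blood totals.** Section 6.3 allows 126 mL and 17.5 mL per visit: 126/18 = 7 and 17.5/2.5 = 7 samples. The caption gives condition 3 one sample at 0830 plus seven from 1000 to 1300, which is eight, or 144 mL and 20 mL.

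**The case against.** The strongest reply is that the trial does not need the gain. At the planned 1 SD power is already about 98%, so adjustment adds 2 points at most; the larger gains appear at 0.6 SD, an effect the documents never mention. That is correct. Against it, Section 8 admits that no data were available to power the outcome, so 1 SD has no empirical support, and interval width matters for the next trial whatever the power here.

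Second, r is unknown. At 0.3 the gain is worth one completer, and r could be lower still if AUC turns out to be incremental. This stands and limits how firmly the point can be pressed.

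Third, the covariate is not the same measurement in all conditions. In conditions 1 and 2 it is also the first point of the AUC; in condition 3 it precedes the OGTT by 90 min. If r in condition 3 were half that elsewhere (assumed), the variance ratio for its contrast would be 0.89 instead of 0.78 at r = 0.5, and 0.76 instead of about 0.52 at r = 0.7. With the clock-time risk in step 5, this stands, and is why the adjusted condition 3 result should not be shown alone.

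Some stronger readings do not hold:

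- A reader might infer that a chance imbalance in fasting glucose undermines the planned comparison. It does not: that chance variation is already in the unadjusted error term.
- A reader might take the omission of diabetes drugs on the test morning as a source of visit-to-visit variation. Sections 6.3 and 9.4 apply it at every visit, so it is constant by design. The replicated diet, 12 h fast and exercise ban also limit such variation.
- A reader might extend the point to insulin, eHSP70, the interleukins, HRV and RMR. No calculation here supports that.

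**Conclusion.** The point holds as a matter of precision. Section 13.2 leaves a scheduled predictor of the primary outcome unused, and no other section brings it in. With 18 completers, adjustment would cut the contrast variance to about 0.95, 0.8 or 0.5 of its unadjusted value at r = 0.3, 0.5 or 0.7. If r is zero it would cost 1 to 2 points of power. These figures assume equal correlation across conditions and exchangeable baselines.

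A reader might infer that the sample size is wrong or that the planned result would be biased. The documents support neither: 13, 18 and 20 all reproduce, and leaving out the covariate widens the interval without shifting the estimate. Nor can it be assumed that adjustment always keeps type I error at 5%. That is secure for condition 2 versus control; for condition 3 it depends on fasting glucose not differing systematically between 0830 and 0930.

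**What to change.** In Section 13.2, pre-specify for glucose AUC and peak a within-participant model with participant, period and condition terms and that visit's pre-heating fasting glucose as covariate. Name the samples: 0 min in conditions 1 and 2, 0830 in condition 3, and never the OGTT time-0 sample of condition 3. Say what happens to the adjustment if the non-parametric fallback in the same section is used.

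As the safeguard, report mean pre-heating glucose by condition and give the unadjusted condition 3 contrast beside the adjusted one. State the reason: the baseline is drawn an hour earlier in that condition.

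Reconcile the seven-sample blood totals in Section 6.3 with the eight samples that the Figure 2 caption lists for condition 3, since the adjustment depends on the 0830 sample, and correct the caption's visit and condition labels.

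The cost is a few sentences and one degree of freedom. No sample is needed beyond those the caption already lists, provided the 0830 draw is confirmed. The choice should be fixed before the data are seen.
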